3.7.3 Vital signs

Vital signs assessments are performed in order to characterize basic body function. The parameters expected to be collected include: height, weight, body temperature, heart rate, and systolic and diastolic blood pressure.

The criteria for clinically notable abnormalities are defined as follows:

Clinically notable elevated values

- Systolic BP: \geq 180 mmHg and an increase \geq 20 mmHg from baseline
- Diastolic BP: \geq 105 mmHg and an increase \geq 15 mmHg from baseline.
- Body temperature: \geq 39.1°C
- Heart rate: \geq 120 bpm with increase from baseline of \geq 15 bpm

Clinically notable below normal values

- Systolic BP: \leq 90 mmHg and a decrease \geq 20 mmHg from baseline
- Diastolic BP: \leq 50 mmHg and a decrease \geq 15 mmHg from baseline
- Body temperature: \leq 35°C
- Heart rate: \leq 50 bpm with decrease from baseline of \geq 15 bpm

The following summaries will be produced for each vital sign parameter:

- Summary statistic for change from baseline to the worst post-baseline value (in both directions, i.e., from baseline to highest post baseline and from baseline to lowest post baseline value).
- Number and percentage of patients with at least one post-baseline vital sign abnormality (in both directions, i.e., both elevated and below normal values).

In addition, patients with clinically notable vital sign abnormalities will be listed by treatment arm. Patients with notable values starting or worsening during the cross-over on-treatment period will be listed separately. The assessments collected later than 30 days after the last treatment date or after the start of cross-over open-label ribociclib plus NSAID plus goserelin treatment will be flagged.

3.7.4 ECG

All analyses of ECG data will be based on the average of all available replicate ECGs at each time point for each patient. For unscheduled assessments, 15-minute windows will be applied to group assessments for averaging.

The following parameters will be assessed: QT, QTcF, QTcB, PR, and QRS intervals in msec, heart rate (bpm), and the overall interpretation if clinically significant abnormalities are present.

- The number and percentage of patients with notable abnormalities will be summarized.
- Summary statistics and shift tables will be presented.
- ECG findings will be listed by treatment
- ECG findings and patients with notable values starting or worsening during the cross-over on-treatment period will be listed separately.

Table 3-2 Clinically notable ECG values

ECG parameter (unit)	Clinically notable criteria
	New > 450
	New > 480
QT, QTcF, QTcB (ms)	New > 500
	Increase from Baseline > 30
	Increase from Baseline > 60
PR duration (ms)	Increase > 25% from baseline and to PR duration > 200, New >200
QRS duration (ms)	Increase > 25% from baseline and to QRS duration > 110, New >110
Heart Rate (bpm)	< 50 and decrease from Baseline of > 25% > 100 and increase from Baseline of > 25%

A newly occurring ECG abnormality is defined as an abnormal post-baseline ECG finding that is not present at Baseline. Baseline is defined as the average of the last ECG measurements (replicates taken on or before date of first dose of study treatment). The percentage of patients having notable ECG interval values is based on the number of patients at risk for the change with a value at baseline and post-baseline.

Subgroup analyses by endocrine combination partner subgroups (tamoxifen and goserelin; NSAI and goserelin) will be performed for clinically notable ECG values.

3.7.5 Cardiac imaging (MUGA / ECHO)

Shift tables comparing baseline to worst post-baseline cardiac imaging (MUGA or ECHO) overall interpretation will be provided. Percentages will be based on all patients in the Safety set.

Note: If there is any change in the methodology used throughout the study compared to baseline, the post-baseline values for which the methodology differs from baseline will be discarded in the tables presenting comparisons to baseline.

Descriptive statistics of the left ventricular ejection fraction (LVEF) at baseline, worst post-baseline value and change from baseline to worst post-baseline value will be provided.

A listing of patients with newly occurring clinically significant abnormality will be produced by treatment arm.

ECG data of patients with abnormal values starting or worsening during the cross-over on-treatment period will be listed separately.

3.7.6 Urinary Analysis

The following parameters will be summarized using a shift table to compare baseline to the worst-post baseline values: urine bilirubin dipstick, urine blood dipstick, urine glucose dipstick, urine ketones dipstick, urine leukocyte dipstick, and urine nitrate dipstick. For all these parameters, both negative and trace are considered as normal and the more pluses, the worse. The urine pH dipstick will be summarized using a shift table with low/normal/high classifications based on laboratory reference ranges.

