  - (i) In the initial rat ADME study cited in previous IB version, thyroid had the highest exposure in albino animals only. As a precaution, thyroid function was monitored in all clinical study protocols. A most recent study (DMPK 1300792) using p.o. dosing in partially pigmented animals with a longer observation period showed the highest distribution to the melanin-containing structures and not to the thyroid gland. In addition, no clinically significant thyroid adverse events have been reported in clinical trials so far. Based on this information, the risk to thyroid gland is removed from the reference safety information for the compound and thyroid laboratory monitoring in clinical protocols are no longer mandated.
  - (ii) In the 15-week rat toxicity study, kidney has been identified as an additional organ of toxicity for LEE011. In order to better characterize this potential side effect, as well as improve the management of the safety of the patients, monthly urinalysis has been added as well as blood urea nitrogen assessment with each chemistry panel.
  - (iii) Revise the treatment allocation in case of prior use of fulvestrant:

In the original protocol, patients who had a last dose of (neo)adjuvant fulvestrant (last dose given <12 months prior to randomization) were eligible to receive tamoxifen +goserelin on study. However, because fulvestrant is an estrogen receptor antagonist with a mechanism of action more similar to tamoxifen than to NSAIs, patients having received (neo)adjuvant fulvestrant (last dose was given < 12 months prior to randomization) will instead be eligible to receive a NSAID + goserelin on study instead of tamoxifen +goserelin.

- (iv) Additional changes:

The assessment of PFS as per blinded independent review committee (BIRC) was changed from a supportive analysis of the primary endpoint to a secondary endpoint.

Updated language has been included in the protocol covering “Discontinuation of Clinical Trial Protocol Elements” in order to maintain consistency with Novartis protocol template language.

Additionally, Amendment 1 includes minor editorial changes, typographical error corrections, and additional clarifications to address investigators’ questions as described in the list of changes below. Lastly, minor changes to the evaluation schedule have been made to allow the screening period to be more efficiently managed.

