#### 1.2.1.1.2 Safety pharmacology and toxicology

*In vivo* cardiac safety studies demonstrated a signal for QT prolongation with the potential to induce incidences of premature ventricular contractions (PVCs) at higher exposure levels.

The effects of LEE011 on the bone marrow (hypocellularity), lymphoid system (lymphoid depletion), intestinal mucosa (atrophy), skin (atrophy), bone (decreased bone formation) and testes (atrophy) are considered to be related to the pharmacological inhibition of cell replication in these tissues due to CDK4/6 inhibition.

[figure not shown]
An increased number of ovarian corpora lutea was observed in a single female dog in the 4-week toxicity study at the highest dose tested (20 mg/kg/day) and this effect could also be related to the pharmacology of LEE011 (arrest of estrous cycle).

The liver, bile system and gall bladder (proliferative changes, cholestasis, sand-like gallbladder calculi and inspissated bile) and the kidney (concurrent degeneration and regeneration of tubular epithelial cells) were identified as additional target organs of toxicity which are not likely related to the primary pharmacology of LEE011.

Inflammatory changes in the lungs of dogs were considered secondary to aspiration of test article and are indicative of the irritant potential of the formulated test-article in the respiratory tract. Correlating hematological and/or biochemistry changes were seen for the effects described in the bone marrow, lymphoid system and liver.

Generally all changes demonstrated either reversibility or a clear tendency towards reversibility. In the rat, there was no evidence of teratogenicity however LEE011 was embryofetotoxic. Data from a rabbit embryofetal development study, shows that LEE011 is teratogenic in the rabbit in the absence of maternal toxicity.

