**Table 7-4 Local clinical laboratory parameters collection plan**

Test Category	Test Name
Hematology	Complete blood count (CBC) including total white blood cell count (WBC) with differential (neutrophil count including lymphocyte, monocyte, eosinophil, and basophil counts) RBC, hemoglobin (Hgb), hematocrit (Hct), and platelet count.
Biochemistry (with fasting glucose)	Total proteins, albumin, total bilirubin, direct bilirubin, indirect bilirubin, AST, ALT, GGT, bicarbonate, calcium, corrected calcium, chloride, creatinine kinase, alkaline phosphatase, amylase, lipase, magnesium, sodium, potassium, urea or BUN, uric acid, serum creatinine, and fasting glucose
Fasting Lipid Panel	Total cholesterol, LDL-cholesterol, HDL-cholesterol and triglycerides (fasting)
Urinalysis	Macroscopic Panel (Dipstick) (Color, Bilirubin, Blood, Glucose, Ketones, Leukocytes esterase, Nitrite, pH, Protein, Specific Gravity, Urobilinogen) If there are any significant findings on the dipstick then a microscopic evaluation should be measured: Microscopic Panel (WBC and RBC sediments, Casts, Crystals, Bacteria, Epithelial cells)
Coagulation	INR
Other Test	FSH, [REDACTED]

Test Category	Test Name
[REDACTED]	

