## **8 Safety monitoring and reporting**

### **8.1 Adverse events**

#### **8.1.1 Definitions and reporting**

An adverse event is defined as the appearance of (or worsening of any pre-existing) undesirable sign(s), symptom(s), or medical condition(s) that occur after patient's signed informed consent has been obtained.

Abnormal laboratory values or test results occurring after informed consent constitute adverse events only if they induce clinical signs or symptoms, are considered clinically significant, require therapy (e.g., hematologic abnormality that requires transfusion or hematological stem cell support), or require changes in study medication(s).

Adverse events that begin or worsen after informed consent should be recorded in the Adverse Events CRF. Conditions that were already present at the time of informed consent should be recorded in the Medical History page of the patient's CRF. Adverse event monitoring should be continued for at least 30 days following the last dose of study treatment. Adverse events (including lab abnormalities that constitute AEs) should be described using a diagnosis whenever possible, rather than individual underlying signs and symptoms. When a clear diagnosis cannot be identified, each sign or symptom should be reported as a separate Adverse Event.

Adverse events will be assessed and graded according to the Common Terminology Criteria for Adverse Events (CTCAE) version 4.03.

If CTCAE grading does not exist for an adverse event, the severity of mild, moderate, severe, and life-threatening, corresponding to Grades 1 - 4, will be used. CTCAE Grade 5 (death) will not be used in this study but is collected as seriousness criteria; rather, information about deaths will be collected through a Death form.

The occurrence of adverse events should be sought by non-directive questioning of the patient (subject) during the screening process after signing informed consent and at each visit during the study. Adverse events also may be detected when they are volunteered by the patient

(subject) during the screening process or between visits, or through physical examination, laboratory test, or other assessments. As far as possible, each adverse event should be evaluated to determine:

1. The severity grade (CTCAE Grade 1-4)
2. Its duration (Start and end dates)

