#### **10.5.3.3 Laboratory abnormalities**

For laboratory tests covered by the Common Terminology Criteria for Adverse Events (CTCAE) version 4.03, the study's biostatistics and reporting team will grade laboratory data accordingly. For laboratory tests covered by CTCAE, a Grade 0 will be assigned for all non-missing values not graded as 1 or higher. Grade 5 will not be used.

In some cases (e.g., white blood cell differentials), the lower limits of normal ranges used in CTCAE definition have to be replaced by a clinical meaningful limit expressed in absolute counts.

For laboratory tests where grades are not defined by CTCAE, results will be graded by the low/normal/high classifications based on laboratory normal ranges.

The following by-treatment summaries will be generated separately for hematology, biochemistry and urinary laboratory tests:

- Frequency table for newly occurring on-treatment grades 3 or 4
- Shift tables using CTCAE grades to compare baseline to the worst on-treatment value
- For laboratory tests where CTCAE grades are not defined, shift tables using the low/normal/high/(low and high)

- Classification to compare baseline to the worst on-treatment value.
- Listing of all laboratory data with values flagged to show the corresponding CTCAE grades and the classifications relative to the laboratory normal ranges.

In addition to the above mentioned tables and listings, other exploratory analyses, for example figures plotting time course of raw or change in laboratory tests over time or box plots might be specified in the analysis plan.

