3.7.7 Other safety data

Data with notable values from other tests will be listed, and any other information collected will be listed as appropriate.

Notable values collected later than 30 days after the last study treatment date or after the start of cross-over open-label ribociclib plus NSAI plus goserelin treatment will be flagged in the listings. Notable values starting or worsening during the cross-over on-treatment period will be listed separately.

4 Details of the statistical analysis

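### Urinalysis shift tables in both SAPs leave out dipstick protein, which the protocol collects

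*SAP*

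**What the plan says.** The SAP file holds two plans, one for the final CSR and one for the primary PFS analysis. Section 3.7.6 of the first and the Urinalysis paragraph in 3.9.2 of the second carry the same list. Baseline-to-worst shift tables are planned for "urine bilirubin dipstick, urine blood dipstick, urine glucose dipstick, urine ketones dipstick, urine leukocyte dipstick, and urine nitrate dipstick". For these items negative and trace count as normal, and more pluses count as worse. Urine pH gets its own low/normal/high shift table. No other urine parameter is named.

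The protocol collects more. The dipstick panel in Table 7-4 ends with "Ketones, Leukocytes esterase, Nitrite, pH, Protein, Specific Gravity, Urobilinogen". Section 10.5.3.3 then says: "The following by-treatment summaries will be generated separately for hematology, biochemistry and urinary laboratory tests". The summaries that follow include shift tables for tests without CTCAE grades, and no urinary item is excluded.

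On purpose, protocol 1.2.1.1.2 reports that "the kidney (concurrent degeneration and regeneration of tubular epithelial cells) were identified as additional target organs of toxicity". The Amendment 1 rationale, citing a 15-week rat study, says "kidney has been identified as an additional organ of toxicity for LEE011. In order to better characterize this potential side effect" and that, partly for that reason and partly to manage "the safety of the patients, monthly urinalysis has been added as well as blood urea nitrogen assessment with each chemistry panel".

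**The concern.** The protocol measures urine protein, gives a renal reason for adding urinalysis, and plans by-arm urinary summaries. The only urinalysis table specified in either SAP then leaves protein out, with no reason given.

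Without a shift table, protein reaches a between-arm comparison only through adverse events. Protocol 8.1.1 sets a threshold for that: abnormal laboratory values "constitute adverse events only if they induce clinical signs or symptoms, are considered clinically significant", or need therapy or a change in study medication. Measured protein that an investigator judges not clinically significant and does not act on would have no planned summary by arm. What is at stake is completeness of the descriptive renal safety output for a drug with a known non-clinical kidney finding.

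**Working it through.** There is no design figure to reproduce. The check is an item-by-item comparison of the collected panel with the two lists.

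| Dipstick item (protocol Table 7-4) | Named in final-CSR SAP 3.7.6 | Named in primary SAP 3.9.2 |
|---|---|---|
| Color | no | no |
| Bilirubin | yes | yes |
| Blood | yes | yes |
| Glucose | yes | yes |
| Ketones | yes | yes |
| Leukocyte esterase | yes | yes |
| Nitrite (written as nitrate in both SAPs) | yes | yes |
| pH | yes, low/normal/high | yes, low/normal/high |
| Protein | no | no |
| Specific gravity | no | no |
| Urobilinogen | no | no |

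Collected: 11. Named in each SAP: 6 plus-graded items + pH = 7. Unnamed: 11 − 7 = 4.

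Next, whether another planned output gives a by-arm summary of measured protein:

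1. **CTC grading.** Appendix 1 of each SAP has no urine protein row, so neither the worst-grade table nor the graded shift tables reach it.
2. **The general rule for ungraded parameters** (final-CSR SAP 3.7.2, primary SAP 3.9.2). It classifies results as low, normal or high against laboratory reference ranges. A plus-graded result does not fit that naturally, and the urinalysis text gives such items their own convention. Urine pH does fit the general rule, yet it is still named. That suggests the urinalysis paragraph is meant as the complete specification for urine tests.
3. **Listings.** The primary SAP lists all laboratory data. The final-CSR SAP specifies a listing of patients with grade 3 or 4 laboratory abnormalities, and 3.7.7 adds "Data with notable values from other tests will be listed, and any other information collected will be listed as appropriate". These are by-patient listings and do not compare arms.
4. **Adverse-event and AESI tables.** These are by arm, but they hold only what passed the reporting threshold in protocol 8.1.1.

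Finally, availability. Urinalysis is a category D assessment in protocol Table 7-1a, and section 7.1 defines D as data entered into the database. No new collection is needed.

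**The case against.** The best counter-argument is that the general rule already covers protein. The bullet on graded shift tables is limited to hematology and biochemistry, while the bullet on ungraded parameters has no such limit. In the primary SAP, Urinalysis sits inside the laboratory section. Protocol 10.5.3.3 also plans urinary shift tables independently. This leaves some ambiguity, but a specific list with its own grading convention, which names even pH, is more naturally read as closed. A programmer working from it would not produce a protein row.

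The table content is delegated to the TFL shells and programming specifications, which are not among the documents. They may include protein. That limits certainty about the consequence, though not about the SAP wording.

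The link from kidney toxicity to dipstick protein is an inference. The Amendment 1 rationale names urinalysis and blood urea nitrogen, not protein, and it is a change-log entry, used here only for the stated purpose. The non-clinical finding is tubular, and proteinuria is not mentioned. Dipstick blood, glucose and leukocytes are still tabulated. This stands, and it keeps the point small.

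The main renal outputs are intact. Serum creatinine is CTC-graded with shift tables in both SAPs, and renal impairment is an AESI grouping in Table 3-7 of the primary SAP. The final-CSR SAP uses whatever groupings are current at analysis. This stands too.

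The primary PFS analysis took place in October 2017, so editing that SAP cannot change its report. The practical effect is on the final CSR.

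**Conclusion.** The point holds as a minor omission. Neither SAP explicitly plans a by-arm summary of measured urine protein, although the protocol collects it and plans urinary summaries with no item excluded. The gap is one row block in one descriptive table per report. No hypothesis test, type I error rate or efficacy conclusion is affected.

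This rests on reading the urinalysis list as complete rather than as a supplement to the general ungraded-parameter rule, and on not assuming that the unseen shells supply the row. If they do, the SAP text should still be brought into line with them. Color, specific gravity and urobilinogen are also unnamed. Protein is singled out because of the renal reason given for urinalysis and because the existing plus-graded rule applies to it directly.

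**What to change.** Add urine protein dipstick to the shift-table list in final-CSR SAP 3.7.6, by treatment arm, under the convention already stated there. Make the same change in primary SAP 3.9.2 for consistency, or, since that analysis is complete, provide the table as a supplementary output. The cost is three words in each SAP and one more row block in an existing table, from data already in the database.

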3.7.7 Other safety data

Data with notable values from other tests will be listed, and any other information collected will be listed as appropriate.

Notable values collected later than 30 days after the last study treatment date or after the start of cross-over open-label ribociclib plus NSAI plus goserelin treatment will be flagged in the listings. Notable values starting or worsening during the cross-over on-treatment period will be listed separately.

4 Details of the statistical analysis

4.1 Duration of follow-up

Study follow-up will be summarized using the following methods:

- Summary of duration between randomization and cut-off date is defined as follows:
 - Randomization (recruitment) period = $(\text{Date of last patient randomized} - \text{Date of first patient randomized} + 1) / 30.4375$ (months)
 - Duration between randomization and data cut-off date = $(\text{Cut-off date} - \text{Date of randomization} + 1) / 30.4375$ (months). This item will be summarized overall.

All summaries will be reported in months.

Appendix 1 CTC grades for laboratory values in Novartis Oncology

CTC grades for laboratory values in Novartis Oncology (based on CTCAE v4.03 – June 2010)

Page 1

Lab test (toxicity)	SI unit	Lab test (NCDS)	Normal ranges (Merck manual, July 2015) and conversion factors	CTC Grades ⁽¹⁾				
				0	1	2	3	4
Hematology								
WBC ↓ WBC ⁽²⁾ (Leukocytosis)	10 ⁹ /L 10 ⁹ /L	WBC WBC	3.9 – 10.7 x 10 ⁹ /L	≥ LLN	< LLN - 3.0 x 10 ⁹ /L -	< 3.0 – 2.0 x 10 ⁹ /L -	< 2.0 – 1.0 x 10 ⁹ /L > 100 x 10 ⁹ /L	< 1.0 x 10 ⁹ /L -
Hemoglobin ⁽²⁾ (Anemia) Hemoglobin ↑	g/L g/L	HGB HGB	120 - 160 g/L or 7.4 - 9.9 mmol/L (F) 140 - 170 g/L or 8.7 – 10.6 mmol/L (M) (16.113 x mmol/L = g/L)	≥ LLN	< LLN - 100 g/L < LLN - 6.2 mmol/L Increase >0-20 g/L above ULN	< 100 - 80 g/L < 6.2 - 4.9 mmol/L Increase >20-40 g/L above ULN	< 80 g/L < 4.9 mmol/L Increase >40 g/L above ULN	- -
Platelets ↓	10 ⁹ /L	PLAT	150 - 350 x 10 ⁹ /L	≥ LLN	< LLN - 75.0 x 10 ⁹ /L	< 75.0 - 50.0 x 10 ⁹ /L	< 50.0 - 25.0 x 10 ⁹ /L	< 25.0 x 10 ⁹ /L
Neutrophils ⁽³⁾ ↓	10 ⁹ /L	NEUT		≥ 2x10 ⁹ /L	< 2.0 - 1.5 x 10 ⁹ /L	< 1.5 - 1.0 x 10 ⁹ /L	< 1.0 - 0.5 x 10 ⁹ /L	< 0.5 x 10 ⁹ /L
Lymphocytes ⁽³⁾ ↓	10 ⁹ /L	LYM		≥ 1.5x10 ⁹ /L	< 1.5 - 0.8 x 10 ⁹ /L	< 0.8 - 0.5 x 10 ⁹ /L	< 0.5 - 0.2 x 10 ⁹ /L	< 0.2 x 10 ⁹ /L
Lymphocytes ↑	10 ⁹ /L	LYM			-	> 4 - 20 x 10 ⁹ /L	> 20 x 10 ⁹ /L	-
Biochemistry								
AST ↑	U/L	AST	0 - 35 U/L or 0 – 0.58 ukat/L (60 x ukat/L = U/L)	≤ ULN	> ULN - 3.0 x ULN	> 3.0 - 5.0 x ULN	> 5.0 - 20.0 x ULN	> 20.0 x ULN
ALT ↑	U/L	ALT	0 - 35 U/L or 0 – 0.58 ukat/L (60 x ukat/L = U/L)	≤ ULN	> ULN - 3.0 x ULN	> 3.0 - 5.0 x ULN	> 5.0 - 20.0 x ULN	> 20.0 x ULN
Total bilirubin ↑	umol/L	BILI	5.1 – 20.5 umol/L or 0.3 – 1.2 mg/dL (17.1 x mg/dL = umol/L)	≤ ULN	> ULN - 1.5 x ULN	> 1.5 - 3.0 x ULN	> 3.0 - 10.0 x ULN	> 10.0 x ULN
Alk. Phosphatase ↑	U/L	ALP	36 - 92 U/L or 0.5 - 1.5 ukat/L (60 x ukat/L = U/L)	≤ ULN	> ULN - 2.5 x ULN	> 2.5 - 5.0 x ULN	> 5.0 - 20.0 x ULN	> 20.0 x ULN
Creatinine ⁽⁴⁾ ↑	umol/L	CREAT	61.9 - 115 umol/L or 0.7 – 1.3 mg/dL (88.4 x mg/dL = umol/L)	≤ ULN	> ULN - 1.5 x ULN	> 1.5 - 3.0 x ULN	> 3.0 - 6.0 x ULN	> 6.0 x ULN
Creatinine kinase ⁽⁴⁾ ↑	U/L	CK	30 - 170 U/L or 0.5 – 2.83 ukat/L (60 x ukat/L = U/L)	≤ ULN	> ULN - 2.5 x ULN	> 2.5 - 5.0 x ULN	> 5.0 - 10.0 x ULN	> 10.0 x ULN
Albumin ⁽²⁾ (Hypoalbuminemia)	g/L	ALB	35 - 55 g/L or 3.5 to 5.5 g/dL	≥ LLN	< LLN - 30 g/L	< 30 - 20 g/L	< 20 g/L	-
Total Cholesterol ↑	mmol/L	CHOL	3.88 – 5.15 mmol/L or 150 - 199 mg/dL (38.67 x mg/dL = mmol/L)	≤ ULN	> ULN - 7.75 mmol/L > ULN - 300 mg/dL	> 7.75 - 10.34 mmol/L > 300 – 400 mg/dL	> 10.34-12.92 mmol/L > 400 – 500 mg/dL	> 12.92 mmol/L > 500 mg/dL
Lipase ↑	U/L	LIPASE	<95 U/L or <1.58 ukat/L (60 x ukat/L = U/L)	≤ ULN	> ULN - 1.5 x ULN	> 1.5 - 2.0 x ULN	> 2.0 - 5.0 x ULN	> 5.0 x ULN
Amylase ↑	U/L	AMYLASE	0 - 130 U/L or 0 – 2.17 ukat/L (60 x ukat/L = U/L)	≤ ULN	> ULN - 1.5 x ULN	> 1.5 - 2.0 x ULN	> 2.0 - 5.0 x ULN	> 5.0 x ULN
Uric acid ⁽²⁾ (Hyperuricemia)	umol/L	URATE	150 - 470 umol/L or 2.5 – 8 mg/dL (59.48 x mg/dL = umol/L)	≤ ULN	> ULN - 10 mg/dL > ULN - 595 umol/L	-	-	> 10 mg/dL > 595 umol/L

ULN = Upper Limit of Normal range; LLN = Lower Limit of Normal range

LAB - CTC grades in Novartis Oncology (26Oct15)

CTC grades for laboratory values in Novartis Oncology (based on CTCAE v4.03 – June 2010)

Page 2

Lab test (toxicity)	SI unit	Lab test (NCDS)	Normal ranges (Merck manual, July 2015) and conversion factors	CTC Grades ⁽¹⁾				
				0	1	2	3	4
Phosphorus ⁽²⁾ (Hypophosphatemia)	mmol/L	PHOS	0.97 – 1.45 mmol/L or 3.0 - 4.5 mg/dL (0.32 x mg/dL = mmol/L)	≥ LLN	< LLN - 2.5 mg/dL < LLN - 0.8 mmol/L	< 2.5 - 2.0 mg/dL < 0.8 - 0.6 mmol/L	< 2.0 - 1.0 mg/dL < 0.6 - 0.3 mmol/L	< 1.0 mg/dL < 0.3 mmol/L
Calcium (corrected) ⁽²⁾ (Hypercalcaemia)	mmol/L	CACALC	2.2 - 2.6 mmol/L or 9 - 10.5 mg/dL (0.2495 x mg/dL = mmol/L)	≤ ULN	> ULN - 11.5 mg/dL > ULN - 2.9 mmol/L	> 11.5 - 12.5 mg/dL > 2.9 - 3.1 mmol/L	> 12.5 - 13.5 mg/dL > 3.1 - 3.4 mmol/L	> 13.5 mg/dL > 3.4 mmol/L
Calcium (corrected) ⁽²⁾ (Hypocalcaemia)	mmol/L	CACALC		≥ LLN	< LLN - 8.0 mg/dL < LLN - 2.0 mmol/L	< 8.0 - 7.0 mg/dL < 2.0 - 1.75 mmol/L	< 7.0 - 6.0 mg/dL < 1.75 - 1.5 mmol/L	< 6.0 mg/dL < 1.5 mmol/L
Magnesium ⁽²⁾ (Hypermagnesaemia)	mmol/L	MG	0.62 – 0.99 mmol/L or 1.5 – 2.4 mg/dL (0.4114 x mg/dL = mmol/L)	≤ ULN	> ULN - 3.0 mg/dL > ULN - 1.23 mmol/L	-	> 3.0 – 8.0 mg/dL > 1.23 – 3.3 mmol/L	> 8.0 mg/dL > 3.3 mmol/L
Magnesium ⁽²⁾ (Hypomagnesaemia)	mmol/L	MG		≥ LLN	< LLN - 1.2 mg/dL < LLN - 0.5 mmol/L	< 1.2 - 0.9 mg/dL < 0.5 - 0.4 mmol/L	< 0.9 - 0.7 mg/dL < 0.4 - 0.3 mmol/L	< 0.7 mg/dL < 0.3 mmol/L
Glucose (non-fasting) ⁽²⁾ (Hyperglycaemia)	mmol/L	GLUCSN	<7.8 mmol/L or <140 mg/dL (0.05551 x mg/dL = mmol/L)	≤ ULN	-	> ULN - 250 mg/dL > ULN - 13.9 mmol/L	> 250 - 500 mg/dL > 13.9 - 27.8 mmol/L	> 500 mg/dL > 27.8 mmol/L
Glucose (fasting) ⁽²⁾ (Hyperglycaemia)	mmol/L	GLUCSF	3.9 – 5.8 mmol/L or 70 - 105 mg/dL (0.05551 x mg/dL = mmol/L)	≤ ULN	> ULN - 160 mg/dL > ULN - 8.9 mmol/L	> 160 - 250 mg/dL > 8.9 - 13.9 mmol/L	> 250 - 500 mg/dL > 13.9 - 27.8 mmol/L	> 500 mg/dL > 27.8 mmol/L
Glucose ⁽²⁾ (Hypoglycaemia)	mmol/L	GLUCSN/ GLUCSF		≥ LLN	< LLN - 55 mg/dL < LLN - 3.0 mmol/L	< 55 - 40 mg/dL < 3.0 - 2.2 mmol/L	< 40 - 30 mg/dL < 2.2 - 1.7 mmol/L	< 30 mg/dL < 1.7 mmol/L
Potassium ⁽²⁾ (Hyperkalemia)	mmol/L	K	3.5 - 5.0 mmol/L (0.2558 x mg/dL = mEq/L = mmol/L)	≤ ULN	> ULN - 5.5 mmol/L	> 5.5 - 6.0 mmol/L	> 6.0 - 7.0 mmol/L	> 7.0 mmol/L
Potassium ⁽²⁾ (Hypokalemia)	mmol/L	K		≥ LLN	< LLN - 3.0 mmol/L	-	< 3.0 - 2.5 mmol/L	< 2.5 mmol/L
Sodium ⁽²⁾ (Hypermnatremia)	mmol/L	SODIUM	136 - 145 mmol/L (0.435 x mg/dL = mEq/L = mmol/L)	≤ ULN	> ULN - 150 mmol/L	> 150 - 155 mmol/L	> 155 - 160 mmol/L	> 160 mmol/L
Sodium ⁽²⁾ (Hyponatremia)	mmol/L	SODIUM		≥ LLN	< LLN - 130 mmol/L	-	< 130 - 120 mmol/L	< 120 mmol/L
Triglyceride ^{(2) †}	mmol/L	TRIG	< 2.82 mmol/L or < 250 mg/dL (0.01129 x mg/dL = umol/L)	< 150 < 1.71	≥ 150 - 300 mg/dL ≥ 1.71 – 3.42 mmol/L	> 300 - 500 mg/dL > 3.42 – 5.7 mmol/L	> 500 - 1000 mg/dL > 5.7 – 11.4 mmol/L	> 1000 mg/dL > 11.4 mmol/L
Coagulation								
INR ^{(2) †}	1	INR	0.8 – 1.2	≤ ULN	> ULN - 1.5 x ULN	> 1.5 - 2.5 x ULN	> 2.5 x ULN	-
Activated partial thromboplastin time ^{(2) †}	sec	APTT	25 - 35 sec	≤ ULN	> ULN - 1.5 x ULN	> 1.5 - 2.5 x ULN	> 2.5 x ULN	-
Fibrinogen ^{(4) †}	g/L	FIBRINO	1.5 – 3.5 g/L or 150 – 350 mg/dL (0.01 x mg/dL = g/L)	≥ LLN	< LLN - 0.75 x LLN	< 0.75 - 0.5 x LLN	< 0.5 - 0.25 x LLN	< 0.25 x LLN

ULN = Upper Limit of Normal range; LLN = Lower Limit of Normal range

- (1) = LAB CTC grades 1, 2, 3, 4 overrule the study specific (central or local) normal range criteria, e.g. if ULN of Sodium is 151 mmol/L and the value is 151 mmol/L, CTC grade 2 is assigned although the value is ≤ ULN.
- (2) = Life-threatening consequences and/or hospitalization are not considered for determination of LAB CTC grades 3 and 4. Concomitant usage of anticoagulation therapy (for INR and Fibrinogen) is not considered either.
- (3) = Values and LNRs for blood differentials can be given as %, absolute values should then be calculated using WBC. Generally, ≥ 1.5 x 10⁹/L (lymphocytes) and ≥ 2 x 10⁹/L (neutrophils) are considered as LAB CTC grade 0
- (4) = For Creatinine and Fibrinogen, the comparison with baseline is not considered for derivation of LAB CTC grades

Clinical Development

